6.2.1. Definition of Dose-Limiting Toxicity

A dose-limiting toxicity (DLT) is defined as any grade 3 or higher non-hematologic adverse event or abnormal laboratory value occurring during the first cycle on study that cannot be attributed by the investigator to a clearly identifiable cause such as disease progression, underlying illness, concurrent illness, or concomitant medication, with the following exceptions:

- Grade 3 nausea, vomiting or diarrhea that can be managed to < Grade 3 within 7 days with standard antiemetic or antidiarrheal medications
- Grade 3 or 4 electrolyte abnormalities will only be considered DLT if possibly related to study drug, extend beyond 72 hours, and are not corrected by optimal replacement therapy. Venetoclax interruption for up to 72 hours following transient (< 48 hours) chemical changes and laboratory TLS may be allowed and may not be considered a DLT.

Confirmed Hy's law cases will be considered as DLT. A positive Hy's law case is defined as AST or ALT $\geq 3 \times$ ULN in the setting of total bilirubin $\geq 2 \times$ ULN, without findings of cholestasis, and no other reason can be found to explain the combination of increased aminotransferases and total bilirubin, such as viral hepatitis A, B, or C, preexisting or acute liver disease, or another drug capable of causing the observed injury.

Hematologic DLT is defined as Grade ≥ 4 neutropenia and/or thrombocytopenia and no greater than 5% marrow blasts lasting for 6 weeks or more after the start of a course in the absence of underlying MDS. Anemia will not be considered for the definition of DLT.

Patients with neutropenia or thrombocytopenia as a consequence of the disease prior to the start of therapy do not require treatment interruptions for myelosuppression. Dose reductions of the study treatment in these patients may be considered on an individual case basis and discussed with the PI.

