2.2. Overview of Treatment

2.2.1. Omacetaxine

OM is a semisynthetic version of a plant alkaloid extracted from *Cephaelotaxus fortunei*, a species of evergreen tree that is indigenous to China. It is available in China for the treatment of hematological malignancies. OM mechanisms of action include protein synthesis inhibition and induction of differentiation and apoptosis.(Boyd & Sullivan, 1984; Huang, 1975) Recent studies indicate OM is affecting histone deacetylase and is also a potent angiogenesis inhibitor. OM has shown activity in AML and other hematologic cancers, including acute promyelocytic leukemia (APL), chronic myeloid leukemia (CML), and MDS. Studies from China reported high response rates in patients with leukemia, trials in the U.S. have shown significant activity as well.(H. Kantarjian et al., 2015; H. M. Kantarjian et al., 2001) In a Phase I-II trial, Warrell et al. treated 49 patients with refractory AML with OM, 5 or 7 mg/m² daily for 7 days and 5 mg/m² daily for 9 days (25-49 mg/m² per course), in a continuous infusion schedule(Warrell, Coonley, & Gee, 1985). Dose escalation beyond 5 mg/m² daily resulted in frequent interruption of OM infusion because of hypotension. Hypotensive episodes occurred in approximately 30% of patients; myalgias occurred in 20% of patients and hyperglycemia in 57% of patients (it was severe in 23%). A schedule of 5 mg/m² daily for 9 days was judged reasonable. Of 28 evaluable patients with AML who were treated with cumulative doses of 45-49 mg/m², 7 (25%) achieved a CR. The recommended dose schedule of OM was 5 mg/m² daily for 9 days.

In another study, Kantarjian et al. investigated OM in a lower dose, longer infusion schedule of 2.5-3 mg/m² by continuous infusion daily for 14-21 days in patients with refractory-recurrent acute leukemia in an attempt to demonstrate efficacy without hypotensive events. While the response rate was low in this AML refractory group of patients, the longer infusion lower daily dose schedule averted cardiovascular toxicity.(H. M. Kantarjian et al., 1989) The summary Phase I-II trials of OM conducted at the Memorial Sloan-Kettering Cancer Center, New York Medical College, and the Eastern Cooperative Oncology Group included 117 patients with

refractory AML treated at doses of 5-7 mg/m² daily by continuous infusion. Among 91 evaluable patients, 14 achieved a CR (15%) and 1 achieved a partial response.

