In the New York Medical College studies, Feldman et al. used OM, 5 mg/m², by continuous infusion daily for 9 days in patients with refractory-recurrent acute leukemia or blastic phase CML.(Feldman et al., 1992) Sixty-six patients were treated; their median age was 41 years. CRs were achieved in 7 of 43 patients (16%) with recurrent AML, in none of 11 patients with AML that primarily was resistant to anthracycline-cytarabine combinations, and in 2 of 3 patients whose disease was resistant to low-dose cytarabine. Side effects included significant hypotensive events, fluid retention, weight gain (29%), and hyperglycemia (63%). Other studies have also demonstrated the activity of OM in AML.

Given the excellent bioavailability of subcutaneous OM and its ability to be administered in the outpatient setting, OM was subsequently developed as a treatment for CML. Based on promising clinical activity in several phase II studies, OM was granted U.S. Food and Drug Administration approval in October 2012 for treatment of adults with chronic- or accelerated-phase CML who are resistant and/or intolerant to two or more tyrosine kinase inhibitors.

Recently, a trial of low-dose omacetaxine for patients with relapsed MDS was performed at our institution at a dose of 1.25 mg/m² subcutaneously twice daily on a 3 day schedule.(Short et al., 2019) Forty two patients were enrolled, with a median age of 76 years. The ORR was 33%, with a median OS of 7.5 months. The most common grade ≥ 3 adverse events were infections (26%), febrile neutropenia (10%), and hemorrhage (7%) Of importance, two patients had ongoing response to OM lasting 2 years or longer, and both patients were noted to have RUNX1 mutations.

We have recently also reported our experience using OM for 3 days in combination with low-dose cytarabine. This combination was found to be safe and effective in inducing an objective response rate of 50% (CR rate of 30%) with a median survival of 9.3 months.

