5.2.1. Table of Events

	Screening		Cycle 1			Cycle 2			Add'l Cycles	End of Study (EOS)	
	Cycle Day	-1	1	8	15	22	1	8	15	22	
Study Day	-14 to 0	1	8	15	22	29	36	43	50	-	
Complete history	X		X			X				X	
Physical examination ^a	X		X			X				X	X
TLS prophylaxis initiation		X									
Document all measurable disease (if present)	X										
CBC with differential ^b	X		X	X	X	X	X	X	X	X	
Creatinine, total bilirubin, ALT and/or AST ^b	X		X	X	X	X	X	X	X	X	
TLS Labs (Creatinine, potassium, Calcium, Uric acid, Phosphorus			X ⁱ								
Pregnancy test ^c	X										
Bone marrow biopsy and aspirate ^d	X					Day 21-28				X ^h	X
correlatives on blood ^e			X	X	X	Day 21-28					X
correlatives on bone marrow ^f	X					Day 21-28				X ^f	X

- a) A complete physical examination will be done on day 1 of each cycle (+/- 7 days).
- b) CBC with differential, creatinine, total bilirubin, ALT or AST will be done at least once weekly (+/- 4 days) for the first 2 cycles, then every 2-4 weeks on subsequent cycles.
- c) Pregnancy test either urine or plasma should be done in women of childbearing potential within 72 hours before initiation of protocol therapy.
- d) Bone marrow biopsy and aspiration must be done within 28-days of initiation of therapy; then after cycle 3, cycle 5, every 3 cycles thereafter, and end of study. Cytogenetics and molecular annotation may be used from prior bone marrow analysis (+/- 28 days) if these were not reported on the screening bone marrow.
- e) Correlative studies will be collected on peripheral blood at Day 0 or Day 1 (prior to dosing), day 2, day 5, day 15, and between days 21 to 28 on cycle 1. Subsequently, peripheral blood will be obtained at progression if possible. Window of +/- 1 day during cycle 1, afterwards window will be +/- 7 days.

- f) Correlative studies will be collected on bone marrow at baseline (prior to dosing), on day 28 (+/- 7 days), and at progression.
- g) EOS visits include a physical examination, CBC with differential and platelets and a limited chemistry profile (total bilirubin, serum creatinine, AST or ALT). A bone marrow aspiration may be done if non-response or progressive disease cannot be unequivocally diagnosed from peripheral blood.
- h) At subsequent cycles, bone marrow (aspiration and/or biopsy) will be performed every 3 cycles at the discretion of the treating physician

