- i) During cycle 1 venetoclax dosing ramp up, TLS lab monitoring (K+, uric acid, Phosphorus, Calcium and Creatinine) should occur at pre-dose, 6-8 hours post dose, and 24 hours post dose (inpatient AM labs may substitute for the 24 hour post-dose labs if applicable).

Correlative Sample Collection and Specifics:

Samples and Studies	Day 0 (prior to starting Ven and OM)	Day 2 (day after starting daily PO Ven but before OM)	Day 5 (At the end of OM treatment)	Day 15 or 22 (after starting therapy and only if AML is without response or progressing)	Day 28 (End of the first cycle of therapy)
Bone marrow aspirate (BMA) sample for NGS, FCM analysis, and Epigenome/transcriptome/proteome analyses	X			X only if AML is without response or progressing	X
Peripheral blood (PB) and/or BMA (if available) (two 8 ml heparinized green-top tubes) samples for harvesting fresh CD34+ mononuclear cells	X	X		X	X
ATAC-Seq and ChIP-Seq analyses on nuclei to determine accessible chromatin SE/E profile	X		X	X	X
RNA-Seq and QPCR analyses on total RNA to determine mRNA expression for gene-sets and signature profile	X		X	X	X
RPPA/Western on cell lysates to determine protein expression profile	X	X	X	X	X
Flow Cytometry on paraformaldehyde fixed cells	X	X	X	X	X
Confocal microscopy on cytopsued paraformaldehyde-fixed cells	X		X	X	X

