5.2.2. Cycle 1 day -1

To mitigate the risk for TLS, subjects must be receiving tumor lysis prophylaxis, including hydration (oral, intravenous) and treatment with a uric acid reducing agent (allopurinol, rasburicase) per institutional guidelines prior to and during the venetoclax ramp-up period of Cycle 1.

5.2.3. Cycle 1 Venetoclax Ramp Up:

Venetoclax will be administered at a dose of 100 mg (or equivalent) on day 1, 200 mg (or equivalent) on day 2, and 400 mg (or equivalent) on day 3-10 of the first cycle or at the RP2D duration.

During cycle 1 venetoclax dosing ramp up, TLS lab monitoring (K+, uric acid, Phosphorus, Calcium and Creatinine) should occur at pre-dose, 6-8 hours post dose, and 24 hours post dose (inpatient AM labs may substitute for the 24 hour post-dose labs if applicable).

No ramp up is required in subsequent cycles.

5.2.4. Treatment Schedule:

All subjects must complete a screening visit, cycle 1 day 1, cycle 1 day 15 visit, day 1 visits for each new cycle, and an end-of-treatment visit.

Patients may remain on study for up to 12 cycles if the patient demonstrates clinical benefit and no excessive toxicity (i.e. no clinically significant non-hematologic study-drug related grade ≥ 3 toxicity). Patients who are experiencing clinical benefit and have not experienced excessive toxicity may be eligible to continue therapy after discussion with the PI and the discussion documented in the patient's medical record.

Bone marrow biopsy and/or aspiration on day 28 (+/- 7 days); if no morphologic evidence of leukemia, venetoclax should be held and bone marrow should be repeated 2 weeks (+/- 7 days) in the absence of count recovery. Bone marrow biopsy and aspiration after cycle 3 and cycle 5; subsequently bone marrow aspirate and/or biopsy, every 3 cycles or as clinically indicated. No repeat bone marrow is necessary if nonresponse or progressive disease can be unequivocally diagnosed from peripheral blood tests.

Cytogenetics should be performed if abnormal pre-therapy, any time a bone marrow exam is performed. Molecular testing depending on the positive tests pre-study (specific mutations, whole genome sequencing) and should be followed any time a bone marrow exam is performed. Omissions will not be considered as deviations.

Multi-parameter flow cytometry for the presence of leukemia associated immunophenotype (minimal residual disease) any time a bone marrow exam is performed. Omissions will not be considered as deviations.

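### Laboratory values that can define a DLT are not all on the cycle 1 schedule (glucose, sodium and magnesium never; potassium, calcium and phosphorus only to about day 4), so DLTs can be missed, and any error favours higher doses

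*Combined protocol and SAP*

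**What the plan says.** **DLT definition (6.2.1).** A DLT is "any grade 3 or higher non-hematologic adverse event or abnormal laboratory value occurring during the first cycle on study", unless the investigator can attribute it to another clear cause. Grade 3-4 electrolyte abnormalities count only if three conditions hold together: they are possibly drug-related, they "extend beyond 72 hours, and are not corrected by optimal replacement therapy". Glucose is not an electrolyte, so it falls under the general clause, which has no duration condition.

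**Scheduled chemistry (5.2.1, footnote b).** "CBC with differential, creatinine, total bilirubin, ALT or AST will be done at least once weekly (+/- 4 days) for the first 2 cycles". From cycle 3 the interval widens to 2-4 weeks.

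**Electrolytes (5.2.1 footnote i, and 5.2.3).** "During cycle 1 venetoclax dosing ramp up, TLS lab monitoring (K+, uric acid, Phosphorus, Calcium and Creatinine) should occur at pre-dose", then at 6-8 and 24 hours after the dose. The ramp-up is "100 mg (or equivalent) on day 1, 200 mg (or equivalent) on day 2, and 400 mg (or equivalent) on day 3-10" of cycle 1, or for the RP2D duration.

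**Background (2.2.1).** Hyperglycemia occurred in 57% of patients in one omacetaxine study (severe in 23%) and in 63% in another. Both used continuous infusion at 5 mg/m² daily or more.

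**Use of DLTs (Section 8).** Cycle 1 DLTs drive the BOIN decisions in each arm. In phase 2, DLTs over the first three cycles feed the toxicity stopping rule.

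**The concern.** The definition relies on values that the schedule does not produce. Sodium, magnesium and glucose are in no scheduled panel, including screening and end of study. Potassium, calcium and phosphorus are not scheduled after the ramp-up, although the DLT window is the whole first cycle. Weekly draws with a window of 4 days either way could not establish 72-hour persistence in any case, and no repeat test is required. Without a baseline glucose, it is also harder to attribute a high value to underlying illness.

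The BOIN rule and the phase 2 rule both treat an unrecorded DLT as no DLT. Errors of this kind therefore do not cancel: they all push toward a higher dose, or toward keeping the current one. Whether a DLT is found would also depend on which patients happened to have extra tests.

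**Working it through.** **1. Definition against schedule, cycle 1**

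| Analyte | Can define a DLT under 6.2.1 | Scheduled in cycle 1 |
|---|---|---|
| Creatinine, total bilirubin, ALT or AST | Yes | Weekly |
| Potassium, calcium, phosphorus | Yes, electrolyte rule | Ramp-up only |
| Sodium, magnesium | Yes, electrolyte rule | No |
| Glucose | Yes, general clause | No |

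Full venetoclax dose is reached on day 3, so the last 24-hour sample falls about day 4. Table 1 continues venetoclax to day 10 (level 0) or day 14 (level +1).

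**2. Which dose step is exposed (Table 1)**
- Level 0 to +1 adds only venetoclax on days 11-14. Electrolyte testing that ends about day 4 cannot detect an effect of those days.
- Level 0 to -1 removes omacetaxine on day 4. Missed hyperglycemia therefore matters mainly by preventing a step down.

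**3. The plan's own figures, reproduced.** With φ = 0.30, φ1 = 0.18 and φ2 = 0.42:
- λe = ln(0.82/0.70) / ln[(0.30×0.82)/(0.18×0.70)] = 0.2365 (plan 0.236)
- λd = ln(0.70/0.58) / ln[(0.42×0.70)/(0.30×0.58)] = 0.3585 (plan 0.359)

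All 27 entries of the BOIN decision table match. Exact enumeration (cohorts of 3, at most 12 patients, start at level 0, stop at 9 if the decision is to stay) gives scenario 3 selection of 0.3/19.4/55.2/25.0% at levels -2/-1/0/+1. The plan states 0.3/19.3/54.5/25.6%. Selection percentages in the other scenarios agree within 2 points. The plan's table assumes that every DLT is seen.

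**4. First cohort, illustrative.** Assumptions, not in the documents: DLT rate 0.15 from other causes, an independent rate h from unscheduled analytes, and none of the latter detected.
- Observed 0/3: 0.85³ = 0.614
- True 0/3 at h = 0.05: (0.85×0.95)³ = 0.527
- True 0/3 at h = 0.10: (0.85×0.90)³ = 0.448
- If half are detected at h = 0.05, observed 0/3: (0.85×0.975)³ = 0.569

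De-escalation needs at least 2 of 3, with probability 3p²(1-p) + p³:
- Observed, p = 0.15: 0.061
- True at h = 0.05, p = 1 - 0.85×0.95 = 0.1925: 0.097

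At h = 0.05 the missed share of all DLTs is (0.1925 - 0.15)/0.1925 = 22%. If half are detected, the observed rate is 1 - 0.85×0.975 = 0.171 and the share is about 11%.

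**5. Whole phase 1b, scenario 3.** Observed rate = true rate × (1 - f) at every level, where f is an assumed missed share.

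| f | Selects level 0 (true 0.30) | Selects level +1 (true 0.47) |
|---|---|---|
| 0 | 55.2% | 25.0% |
| 10% | 51.2% | 34.2% |
| 20% | 45.2% | 44.6% |

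**6. Phase 2 toxicity rule.** Exact enumeration of the AML and MDS stopping tables in cohorts of 6 reproduces the stated acceptance rates. AML scenarios 1-4 give 10.2/74.1/15.9/0.8% (plan 10.44/73.93/15.88/0.77%). MDS scenarios 1-4 give 9.3/65.0/12.5/0.6% (plan 9.77/65.36/12.85/0.69%).

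Now take true toxicity 0.25, with efficacy and toxicity independent. If one event in five is missed, the observed rate is 0.25×0.8 = 0.20. The chance of declaring the treatment acceptable then rises from 16.2% to 32.3% in AML (response 0.40) and from 12.5% to 26.1% in MDS (response 0.30).

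**The case against.** Several points on the other side stand.

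- **Missed events are not certain.** A reader might infer that these DLTs would be found only by chance. The documents do not support that. Section 7.5.1 requires adverse event monitoring of all subjects, SAEs are captured, footnote b sets a minimum frequency, and symptoms or unscheduled tests can reveal an event. However, 7.5.1 says only that assessments may include laboratory findings. It names no analyte and no timing, so it does not close the gap.
- **The electrolyte rule is narrow.** All three conditions must hold, and failure of replacement presupposes a detected event. Fewer events qualify than a bare 72-hour rule would suggest.
- **Ramp-up sampling overlaps omacetaxine.** Potassium, calcium and phosphorus are sampled through about day 4, which covers omacetaxine days 2-4. For these three analytes the gap is later in the cycle.
- **The 23% is not a usable rate here.** It came from 25-49 mg/m² per course by infusion, against 1.25×2×3 = 7.5 mg/m² per cycle at level 0, and severe is not shown to mean CTCAE grade 3. Section 2.2.1 also reports 42 patients on 1.25 mg/m² twice daily for 3 days. Their most common grade 3 or higher events were infections, febrile neutropenia and hemorrhage; hyperglycemia is not listed. This favours small h without showing that it is zero.
- **Missed hyperglycemia does not raise the omacetaxine dose through escalation.** Levels 0 and +1 have the same omacetaxine schedule.
- **Hy's law is not part of the gap.** A reader might add it, because alkaline phosphatase is not collected. But the definition is met by either transaminase with total bilirubin, and both are scheduled weekly. Missing evidence of cholestasis would tend to leave a case counted as a DLT, which is not an undercount.
- **There are other safeguards.** IND Office approval precedes dose changes, and the RP2D does not rest on BOIN alone. These reviews still work from the recorded DLTs.

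**Conclusion.** The mismatch is in the text, and no other section closes it. DLTs based on glucose, sodium or magnesium at any time in cycle 1, or on potassium, calcium or phosphorus after about day 4, can be missed by a site that follows the schedule exactly. The direction of the error is certain: toward escalating or not de-escalating in phase 1b, and toward continuing in phase 2.

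The size is unknown. The documents give neither the rate of such DLTs at this regimen nor the share that would be detected. The low end looks more realistic: at an assumed h of 0.05, 0/3 is observed 61% of the time against 53% truly if none are detected, or 57% if half are. The scenario 3 and phase 2 figures show sensitivity to an assumed missed share of all DLTs. They are not estimates, because renal, hepatic and symptomatic DLTs would be captured. The documents do not show that dose selection is in fact biased by any given amount. The change is worth making because it is cheap and the definition drives dose selection.

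**What to change.** Reconcile 5.2.1 and 5.2.3 with 6.2.1, so that every analyte that can define a DLT is measured in all patients:

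- Add glucose, sodium, potassium, calcium, phosphorus and magnesium at screening, to the weekly cycle 1 draws in footnote b, and to the chemistry draws within the three-cycle DLT window of phase 2.
- Add glucose to the TLS draws already taken during the omacetaxine days. The weekly draw alone need not fall within days 2-4.
- For any grade 3-4 electrolyte value, require a repeat at or just after 72 hours. A repeat before that time cannot show persistence beyond it.

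The cost is a few more analytes on existing draws and an occasional repeat test, with no new scheduled visit. The observed DLT rate may rise slightly. Weekly sampling can still miss brief events, but ascertainment would then be the same for all patients.

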6.2.2 Serious Adverse Event (SAE) Reporting Requirements for M D Anderson Sponsored protocol

An adverse event or suspected adverse reaction is considered "serious" if, in the view of either the investigator or the sponsor, it results in any of the following outcomes:

- Death
- A life-threatening adverse event
- Inpatient hospitalization or prolongation of existing hospitalization
- A persistent or significant incapacity or substantial disruption of the ability to conduct normal life functions.
- A congenital anomaly/birth defect.

Important medical events that may not result in death, be life-threatening, or require hospitalization may be considered a serious adverse drug experience when, based upon appropriate medical judgment, they may jeopardize the patient or subject and may require medical or surgical intervention to prevent one of the outcomes listed in this definition.

Examples of such medical events include allergic bronchospasm requiring intensive treatment in an emergency room or at home, blood dyscrasias or convulsions that do not result in inpatient hospitalization, or the development of drug dependency or drug abuse (21 CFR 312.32).

- Important medical events as defined above, may also be considered serious adverse events. Any important medical event can and should be reported as an SAE if deemed appropriate by the Principal Investigator or the IND Sponsor, IND Office.
- All events occurring during the conduct of a protocol and meeting the definition of a SAE must be reported to the IRB in accordance with the timeframes and procedures outlined in "The University of Texas M. D. Anderson Cancer Center Institutional Review Board Policy on Reporting Adverse Events for Drugs and Devices".

- Serious adverse events will be captured from the time of the first protocol-specific intervention, until 30 days after the last dose of drug or protocol specific timeline, unless the participant withdraws consent.
- Serious adverse events must be followed until clinical recovery is complete and laboratory tests have returned to baseline, progression of the event has stabilized, or there has been acceptable resolution of the event.
- All SAEs, expected or unexpected/ initial or follow up, must be reported to the IND Office **within 5 working days of knowledge of the event** regardless of the attribution.
- Death or life-threatening events that are unexpected, possibly, probably or definitely related to drug must be reported (initial or follow up) to the IND Office **within 24 hours of knowledge of the event**
- Additionally, any serious adverse events that occur after the 30 day time period or protocol specific timeline that are related to the study treatment must be reported to the IND Office. This may include the development of a secondary malignancy.
- The electronic SAE application (eSAE) will be utilized for safety reporting to the IND Office and MD Anderson IRB.
- All events reported to the supporting company must also be reported to the IND Office

Reporting to FDA:

- Serious adverse events will be forwarded to FDA by the IND Sponsor according to 21 CFR 312.32.
It is the responsibility of the PI and the research team to ensure serious adverse events are reported according to the Code of Federal Regulations, Good Clinical Practices, the protocol guidelines, the sponsor's guidelines, and Institutional Review Board policy.

The Investigator will communicate the occurrence of any serious adverse events which they believe to be definitely, likely, possibly or probably related to the investigated study product(s), and any exposure of a pregnant study participant to the investigated study product(s), within 24 hours of becoming aware of the event to the supporting drug company, TEVA Pharmaceuticals either via email: [contact] or [contact].

6.3 Exploratory Biomarker Analysis:

Peripheral blood and bone marrow aspirate samples will be obtained at study specified time points. Biomarker assays include the following:

